4.4 Multiplicity Strategy

Multiplicity is not an issue since there is only a single primary endpoint. The hypothesis testing is not planned for the secondary endpoints [REDACTED].

4.6 Interim Analysis for Efficacy

No interim analysis is planned.

5 Safety Analysis Strategy

5.1 Safety Endpoints

The safety endpoints are:

- Adverse events including secondary surgical intervention (SSI)
- Device deficiencies
- Posterior capsular opacification
- Posterior capsulotomy
- IOL position change (tilt and decentration)
- Intraocular pressure
- Surgical problems
- Slit Lamp Examination
- Dilated Fundus Examination
- IOL Observations

5.2 Safety Hypotheses

There are no formal safety hypotheses in this study. The focus of the safety analysis will be a comprehensive descriptive assessment of safety endpoints listed in Section 5.1.

5.3 Statistical Methods for Safety Analyses

Except otherwise stated, the analysis set for all safety analyses is the safety analysis set as defined in Section 2.2. Baseline will be defined as the last measurement prior to exposure to investigational product, except otherwise stated.

5.3.1 Adverse events including secondary surgical intervention (SSI)

The number and percentage of eyes with ocular adverse events (including secondary surgical interventions not-related to the optical properties of the IOL) will be presented. Also, the number and percentage of subjects with non-ocular adverse events will be presented. An eye with multiple ocular AEs of the same preferred term is only counted once toward the total of this preferred term.

Adverse events will be summarized in the following tables:

- All Adverse Events (Serious and Non-Serious Combined)
 - Ocular
 - Non-Ocular
- All Adverse Device Effects
 - Ocular
 - Non-Ocular
- All Serious Adverse Events (including Serious Adverse Device Effects)
 - Ocular
 - Non-Ocular
- Subject data Listings
 - Non-Serious Ocular
 - Non-Serious Non-Ocular
 - Serious Ocular
 - Serious Non-Ocular

Also, a patient listing will be provided for adverse experiences occurred from informed consent to exposure to the test article.

5.3.2 Device Deficiencies

A frequency table showing counts for each Device Deficiency category will be presented. In addition, a listing all device deficiencies, as recorded on the Device Deficiency Form will be provided.

5.3.3 Posterior Capsular Opacification

The number and percentage of eyes within each category of subjective posterior capsule opacification will be tabulated by visit. A listing of all posterior capsular opacification data will be provided with the following variables: subject, visit, eye and posterior capsular opacification including none.

5.3.4 Posterior Capsulotomy

The number and percentage of eyes with posterior capsulotomy will be tabulated. A listing of all posterior capsulotomy data will be provided with the following variables: subject, visit, eye, posterior capsulotomy was performed/not performed, date of the procedure and size.

5.3.5 IOL Position Change (tilt and decentration)

Descriptive statistics (numbers and percentages) on eyes in IOL position category (Tilted, Decentered) will be presented. In addition, a listing of subjects with IOL position change including no change will be provided. The listing will include the following variables: subject, visit, eye and no change/amount of tilting or decentration.

5.3.6 Intraocular Pressure

Intraocular pressure (IOP) measurements will be recorded in mmHg. Descriptive summaries (mean, standard deviation, N, median, minimum and maximum) of observed values and change from baseline values will be presented at each study visit. A listing will be provided which presents all eyes with an increase or decrease in IOP of more than 10 mmHg at any visit compared to the same eye at baseline. The listing will include the following variables: subject, age, sex, visit, eye, baseline value, value at the visit and a change from baseline value. Also a listing including all intraocular pressure data will be provided.

5.3.7 Surgical Problems

Descriptive statistics (numbers and percentages) on eyes with surgical problems will be presented. A listing of all eyes will be presented by subject, eye, with/without surgical problem and description of surgical problem.

5.3.8 Slit Lamp Examination

For each slit-lamp parameter, number and percentage of each category will be provided by visit. A listing will be provided for all slit-lamp data at all visits with the following variables: subject, visit, eye and normal/abnormal findings at the visit.

5.3.9 Dilated Fundus Examination

For each dilated fundus parameter, number and percentage of each category will be provided by visit. A listing will be provided for all fundus parameter at all visits. The listing will include the following variables: subject, visit, eye and normal/abnormal findings at the visit.

5.3.10 IOL Observations

IOL observations will be summarized using descriptive statistics, including frequency (N) and percent of eyes at any post-operative visit. A listing will be provided for all IOL observation data at all visits with the following variables: subject, visit, eye, IOL observation including specifying text of other IOL observation at the visit and evaluation of clinical significance.

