## **7 INVESTIGATIONAL PLAN**

### **7.1 Study Design**

This study is a prospective, single-center and non-comparative study. The study will include subjects must be  $\geq 20$  years of age with cataract who would be eligible to receive a TFNT20 lens in at least one eye based on a new Alcon Toric calculator that incorporates ocular trends in Toric IOL planning. Subject with no ocular pathology that could confound study outcome, must require clear cornea cataract extraction, and must desire an IOL that provides the potential for near, intermediate and distance vision and corrects astigmatism. Potential subjects will be screened for enrollment into this clinical trial. Those qualifying will attend a total 5 visits, 1 is preoperative, 1 is operative and 3 are postoperative visits. If the test products will be implanted to both eye, the maximum number of visits is 9 visits, 1 is preoperative, 2 are operative and 6 are postoperative visits. Unscheduled visits may be attended if needed for medical attention.

An overview of the study design is depicted in Figure 7-1.

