### **10.1.2 Surgery Day (Visit 00/00A)**

Record surgical information at Visit 00/00A. If subjects wish to be implanted into both eyes with TFNT20, obtain consent in continuation of the study from each subject prior to the surgery on the 2nd eye.

- Operative eye  
Indicate which eye is being implanted.
- Exclusion criteria during surgery  
Assess qualification according to the inclusion/exclusion criteria during the surgery. The incision site for this study is defined as temporal ( $\pm 15^\circ$ , or approximately 1 mm, for the horizontal meridian (OS:  $0^\circ$ , OD:  $180^\circ$ )).
- Final incision size  
Indicate final incision size (mm) to the nearest 0.1 mm.
- Problems during surgery

Indicate what problems, if any, occurred during surgery. If any exclusion criteria occur, discontinue the subject from the clinical study.

[figure not shown]
- Other procedures at this surgery  
Any other procedures performed at this surgery should be indicated. Since other procedures at this surgery are included in the exclusion criteria, discontinue the subject from the clinical study.
- Lens information  
Provide the IOL information (IOL model, refractive power, serial No.) also in the event of discontinuation of implant. Attach the adhesive label contained in the package of the investigational lens to the Study Participants Card.
- IOL axis orientation (dilated)  
Record the orientation (in degrees; 0 ~180 degrees) of the investigational lens axis (designated by indentations on the IOL optic). [REDACTED]  
[REDACTED]
- Medical history  
Confirm systemic and ophthalmologic complication, ophthalmologic surgical history.
- Concomitant medications  
Indicate the concomitant ocular medications used during the surgery.
- IOL observation  
Observe the IOL surface and the inside of the haptic and optic of the investigational lens with a slit-lamp microscope, and record the presence/absence of visible abnormal findings (debris on IOL surface, forceps marks on IOL surface, IOL discoloration, IOL opacities, IOL scratch, membrane generated on IOL, pigmentation on IOL, surface haze, other.). And regarding the observed findings, evaluate the clinical significance. If the problem may negatively affect postoperative visual acuity, etc., handle it as the clinical significant, and if possible, take photos.
- Adverse events, Device deficiencies  
Presence/absence of adverse events and device deficiencies are recorded since informed consent.
- Secondary surgical intervention

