## 12.6 Safety Analyses

The safety endpoints are:

- Adverse events including secondary surgical intervention (SSI)
- Device deficiencies
- Posterior capsular opacification
- Posterior capsulotomy
- IOL position change (tilt and decentration)
- Intraocular pressure
- Surgical problems
- Slit Lamp Examination
- Dilated Fundus Examination
- IOL Observations

Patient listings will be provided for adverse experiences occurred from informed consent to exposure to the test article. Safety variables above will be analyzed using Treatment-Emergent Safety Analysis Set. For continuous variables, descriptive statistics (mean, standard deviation, N, median, min and max) will be provided for actual value and change from baseline at each visit. For categorical variables, N and percent will be provided for each category at each visit.

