2.2 Safety Analysis Set

The treatment-emergent safety analysis set will include all eyes with attempted implantation with the test article (successful or aborted after contact with the eye).

3 Subject Characteristics and Study Conduct Summaries

For all analysis datasets (Safety Analysis Set, AAS and BAS), demographics (sex, age [<60 , $60-69$, $70-79$, ≥ 80 years], systemic complication [None/Yes, details] and past ocular surgery [None/Yes, details]) will be summarized with the number and percent of subjects in each category for the variable. Age will also be summarized with descriptive statistics (mean, standard deviation, number of subjects or eyes, median, min and max).

4 Efficacy Analysis Strategy

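### The IOL-observation summary in SAP 5.3.10 leaves out the surgery day and pools the later visits, although Protocol 12.6 calls for a by-visit table; the effect is minor

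*SAP*

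**What the plan says.** **Protocol, collection.** Section 10.1.2 makes IOL observation a surgery-day procedure: "Observe the IOL surface and the inside of the haptic and optic of the investigational lens with a slit-lamp microscope". The investigator is then to "record the presence/absence of visible abnormal findings (debris on IOL surface, forceps marks on IOL surface, IOL discoloration, IOL opacities, IOL scratch" and several further findings, and to judge their clinical significance. Section 10.1.3 repeats the same examination at Visits 1/1A, 2/2A and 3/3A. Table 3-1 marks IOL observations at Visits 00/00A, 1/1A, 2/2A and 3/3A.

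**Protocol, analysis.** Section 12.6 names IOL observations as a safety endpoint and sets the general rule: "For categorical variables, N and percent will be provided for each category at each visit".

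**Protocol, visit classes.** Section 7.1 divides the five visits for one eye as follows: "1 is preoperative, 1 is operative and 3 are postoperative visits".

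**SAP, analysis.** Section 5.3.10 gives the summary rule: "IOL observations will be summarized using descriptive statistics, including frequency (N) and percent of eyes at any post-operative visit". It continues: "A listing will be provided for all IOL observation data at all visits with the following variables", and those variables include the visit, the eye and the evaluation of clinical significance. Section 2.2 defines the safety set as "all eyes with attempted implantation with the test article (successful or aborted after contact with the eye").

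**The concern.** The SAP table is narrower than the protocol's rule in two ways. It drops a visit at which the data are collected, and it replaces a by-visit summary with one count over the remaining visits. The dropped visit is the first at which the implanted lens is examined, and the findings to be recorded there include "forceps marks on IOL surface, IOL discoloration, IOL opacities, IOL scratch" and surface debris.

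At stake is the completeness of one descriptive safety table. A finding present on the surgery day and absent later would not be counted. A reader of the table alone could not tell an early finding that cleared from one that appeared at the last visit.

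**Working it through.** The plan gives no figure on this point, so the check compares the texts and counts visits.

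**Step 1: is the surgery day a scheduled observation point?** Yes. Protocol 10.1.2 describes the examination and Table 3-1 marks it at Visit 00/00A.

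**Step 2: can the SAP's term postoperative include the surgery day?** No. Protocol 7.1 counts one operative and three postoperative visits per eye, and the heading of 10.1.3 names the postoperative examinations as Visits 1/1A, 2/2A and 3/3A. If the word any in SAP 5.3.10 were read as each, the pooling complaint would fall away, but Visit 00/00A would still be outside the table.

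**Step 3: count the coverage per eye.**

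| | Visit 00/00A | Visit 1/1A | Visit 2/2A | Visit 3/3A |
|---|---|---|---|---|
| Scheduled (Protocol Table 3-1) | yes | yes | yes | yes |
| Summary under Protocol 12.6 | own N and % | own N and % | own N and % | own N and % |
| Summary table, SAP 5.3.10 | not included | pooled | pooled | pooled |
| Listing, SAP 5.3.10 | yes | yes | yes | yes |

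Scheduled points: 1 + 3 = 4. Points in the SAP table: 4 − 1 = 3. These are counts of visits, not of lost findings.

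**Step 4: which findings are actually missing from the table?** A scratch or forceps mark that persists on an implanted lens can be recorded again at Visits 1 to 3, and then it counts. What drops out is a finding recorded only on the surgery day: one that clears before Visit 1, or one in an eye with no later IOL observation.

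**Step 5: size.** The documents give no number of surgery-day-only findings. As an assumption for scale only, take 30 eyes (the planned minimum in Protocol 12.8) and let k eyes have such a finding. A count that included the surgery day would be higher by k/30: 0% for k = 0, 1/30 = 3.3% for k = 1, and 2/30 = 6.7% for k = 2. Nothing in the documents favours any of these values.

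**Step 6: compare the other SAP safety sections.** Capsular opacification (5.3.3), slit lamp (5.3.8) and fundus (5.3.9) are tabulated by visit, and intraocular pressure (5.3.6) is summarised at each visit. Capsulotomy (5.3.4) and IOL position change (5.3.5) do not mention visits in their tabulation, but Table 3-1 schedules both only after surgery. Among these examination findings, 5.3.10 is the one whose wording excludes a scheduled visit, and the SAP gives no reason for it.

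**The case against.** The strongest reply is that nothing is lost from the report. The listing covers all visits and carries the significance judgement. In a single-site study of about 30 subjects, a reader can see in it every surgery-day finding and whether it cleared. This stands and is the main reason the point is minor. It does not remove the mismatch, because a listing is not the N and percent by visit that Protocol 12.6 specifies.

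A second reply is that a count of eyes ever affected after surgery is a usual safety summary, and that the SAP's description of the statistics is not worded as exhaustive. The count is reasonable as an additional row. As the only summary described, it does not meet the protocol's rule.

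Three stronger readings are tempting, and the documents do not support them:

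- **Lens damage at implantation would go unreported.** The listing includes the surgery day, and lasting damage can be recorded again later. Surgical problems (SAP 5.3.7) and device deficiencies (SAP 5.3.2) also have their own tables and listings. The documents do not say that every IOL observation would be captured there, but they do not show that it would be missed.
- **An eye whose lens touched the eye and was withdrawn would count as zero.** Such an eye is in the safety set. However, Protocol 10.1.2 asks for lens information when implantation is discontinued and has no matching clause for IOL observation. Whether a withdrawn lens is observed at all is not stated. SAP 5.3.10 also names no denominator, so the eye's effect on the percentage is unknown.
- **The SAP must tabulate clinically significant findings separately.** The protocol requires that significance be evaluated, and the SAP lists it. Neither document calls for a separate table row.

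**Conclusion.** The mismatch is established on the text. SAP 5.3.10 summarises three of the four scheduled observation points as one pooled count, where Protocol 12.6 calls for a summary at each visit and the protocol collects surgery-day data. The table omits findings seen only on the surgery day and does not show findings by visit.

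The consequence is small. It concerns one descriptive safety table. SAP 5.2 sets no formal safety hypotheses, the full data are listed, and the primary analysis and sample size do not depend on it. The visit count rests on Table 3-1 and Protocol 7.1. The percentages in the working rest on an assumed number of eyes and should not be quoted as an expected error.

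**What to change.** Amend SAP 5.3.10 so that the table gives the number and percentage of eyes with each IOL observation by visit, including Visit 00/00A, with eyes examined at that visit as the denominator. Keep the count over any postoperative visit as an additional line. A further row for clinically significant observations is optional.

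The cost is a change of SAP wording and one table shell. The data are already collected at all four points and already planned for the listing, so no new assessment or case report form item is needed.

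If the sponsor prefers to leave the surgery day to the listing, the SAP should say so and give the reason for departing from Protocol 12.6.

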5.4 Interim Analysis for Safety

No interim analysis is planned.

6 Pharmacokinetic Analysis Strategy

Not Applicable.

7 Analysis Strategy for Other Endpoints

Not Applicable.

8 Sample Size and Power Calculations

To enroll more than or equal to 30 eligible T2 eyes used for analysis, at least 30 subjects will be evaluated by a new Alcon Toric calculator and unilaterally or bilaterally implanted with the AcrySof IQ PanOptix IOL (TFNT20).

Using a new Alcon calculator, percentage of eyes with ≤ 0.25 D refractive cylinder at Visit 3/3A (Day 30-60) in T2 group was estimated as 60.9% based on a previous [REDACTED] (T2) study conducted in US. Using the same calculator, the percentage in T0 group was recalculated as 29.2% from the combined result of studies (non-Toric T0 lenses) conducted in Japan [REDACTED]. Statistical test will be conducted to compare percentage of T2 with a constant of 29.2% as percentage of T0. With 30 eyes from 30 subjects in T2 group, assuming the percentage of T2 is equal to 60.9% [REDACTED] the statistical power to demonstrate superiority of T2 to T0 is 91.6% with one-sided alpha of 2.5%, using an exact test of binomial proportion.

9 References

No references.

10 Revision History

This is the original (Version 1.0) Statistical Analysis Plan for this study. This version of the Statistical Analysis Plan is based on Version 2.0 of the study protocol.

Signature Page for V-CLN-0002915 v1.0

Signature Page for V-CLN-0002915 v1.0
